Medical condition or disease under investigation	Investigation of endodontically treated teeth's success and survival rate at 1-2 years post treatment.
Purpose of clinical trial	To compare the success and survival rate of endodontically treated teeth and restoration with varying degrees of tooth structure loss restored with CAD CAM restorations
Primary objective	To investigate whether varying amounts of residual tooth structure have an influence on the success and survival rate of endodontically treated teeth and restoration at 1-2 years post treatment restored using CAD CAM restorations
Secondary objective (s)	To assess the survival of the CAD CAM restorations on root canal treated teeth and determine the main types of failure.
Trial Design	Case control
Sample Size	120patients
Summary of eligibility criteria	Patients either male or female over the age of 18 in good general health needing root canal treatment.
Version and date of final protocol	Version 1.6 date: 29-06-2017

1. Background & Rationale

Enlargement and shaping of the root canal space are the main objectives of root canal treatment, then sealing it in 3 dimensions to avoid any infection in the future [1, 2]. Wide range of instruments and techniques have been used to accomplish root canal treatment [3].

Although initial root canal therapy has been shown to be a predictable procedure with a high degree of success [4-7], failures can occur after treatment. Recent publications reported failure rates of 14%–16% for initial root canal treatment [4, 6-8].

Lack of healing is attributed to persistent intraradicular infection residing in previously uninstrumented canals, dentinal tubules, or in the complex irregularities of the root canal system [9-12]. The extraradicular causes of endodontic failures include periapical actinomycosis [13], a foreign body reaction caused by extruded endodontic materials [14, 15], an accumulation of endogenous cholesterol crystals in the apical tissues [16], and an unresolved cystic lesion [17, 18]. The preferred treatment of failing endodontic cases is nonsurgical retreatment. According to [6, 19-22] this treatment usually results in successful outcomes.

Conflicting results are present in the literature in relation to the survival of endodontically re-treated teeth. Well controlled trials at 4 years [23] did not find any significant difference between survival of root canal treated and root canal re-treated teeth, whereas the comparison of epidemiologic studies conducted on the survival of teeth following primary and secondary endodontic treatment in dental practices [7, 24] shows that many more re-root canal treated teeth are extracted in the long term. The only information available on the effect of the restoration type on the survival of re-root canal treated teeth is that teeth restored with a cast restoration and teeth not requiring a post for the retention of the crown survive longer. Advances in technology, materials and techniques offer more contemporary ways to restore endodontically treated teeth. One of them is the computer aided design and computer aided manufacturing of ceramic onlays and crown. While this is an established and successful treatment for vital teeth, there are no randomised clinical trials showing its efficacy in endodontically treated teeth.

Cone beam computed tomography (CBCT) is a contemporary, radiological imaging system designed specifically for use on the maxillofacial skeleton. The system overcomes many of the limitations of conventional radiography by producing undistorted, three-dimensional images of the area under examination. These properties make this form of imaging particularly suitable for use in endodontics [25]. Recent laboratory and clinical investigations have revealed that periapical disease may be detected sooner using CBCT compared with periapical views and the true size, extent, nature and position of periapical and resorptive lesions can be assessed [26].

This CBCT study will compare the success and survival rate of endodontically treated teeth with varying degrees of tooth structure loss restored with CAD CAM (Computer Aided Design Computer Aided Manufacturing) restorations, which are routinely used for the clinical care of patients.

This will be carried out at KCL Dental Institute at Guy's Hospital and will form part of the routine dental treatment done at the dental clinics. Potential volunteers will be given written information about the process (see attached information sheet) and be given time to consider participation. Once any questions have been answered, fully informed written consent will be obtained if they are interested in taking part.

Patients requiring endodontic treatment with varying degrees of tooth structure loss will be detected and diagnosed and treated by endodontic McInDent postgraduate students at Guy's hospital using suitable clinical techniques.

Immediately after root canal treatment has been completed and at patients' review appointments in addition to the conventional radiograph we would also take an additional specialised 3-dimensional Cone Beam Computed Tomography (CBCT) scan of the tooth. Clinical evaluation and radiographic assessment including dental periapical radiograph and Cone Beam Computed Tomography (CBCT) scans will be done at baseline, 12 months and 24 months.

There are no side effects of taking part in this study other than those expected from exposure to ionising radiation taken during routine operative dental care. Every exposure to ionising radiation carries a risk, but due to the low doses of radiation from dental radiology including CBCT, this risk is negligible. The effective dose of a conventional radiograph and a cone beam computed scan is 5 μ Sv and 66 μ Sv (micro Sieverts) respectively, equivalent to 0.19% and 2.43% annual background radiation respectively.

The total radiation dose corresponds to approximately 28 days equivalent natural background radiation, where background radiation is approximately 2.7 mSv per year in the UK.

This clinical trial will be conducted in compliance with the principles of the Declaration of Helsinki. The protocol will be submitted for approval to an NHS Research Ethics Committee.

2. Trial Objectives, Design and Statistics

2.1. Trial Objectives

Aims and Objectives:

The clinical trial aims to investigate whether varying amounts of residual tooth structure have an influence on the success and survival rate of endodontically treated teeth and/or restoration at 1-2 years post treatment by using Cone Beam Computed Tomography (CBCT).

Primary and Secondary endpoints:

The principal outcome of the study is to assess the success and survival of endodontically treated teeth and restoration at 1 and -2 years post treatment restored using CAD CAM restorations. The secondary outcome measure is to assess the survival of the CAD CAM restorations on root canal treated teeth and determine the main types of failure.

2.2 Trial Design & Flowchart

The study is a case control comparing the success and survival rate of endodontically treated teeth with varying degrees of tooth structure loss restored using CAD CAM restorations.

[figure not shown]
Patients requiring endodontic treatment will be assessed clinically and radiographically and divided into groups defined according to the residual coronal dentin after root canal treatment into four groups (less than 33% , 33%-50%, 50%-66% and more than 66% of tooth structure remaining). The endodontic treatment and final restoration will be accomplished by Endodontic McInDent Postgraduates Students (Endodontic Postgraduate Unit, Guy's Hospital, Guy's & St. Thomas' NHS trust) who will be trained

to ensure standardisation of the endodontic and operative procedures by using one of the indirect/direct restorations.

Dental periapical radiograph and Cone Beam Computed Tomography (CBCT) scans will be taken at baseline, 12 months and 24 months. The patients will be sent a reminder to attend the follow up by email, letter or SMS. Clinical assessment and radiographical evaluation of Cone Beam Computed Tomography (CBCT) scans will be carried out immediately after endodontic treatments have been accomplished and 1 and 2 years post operatively and will be assessed independently by a group of examiners.

Four examiners (Endodontists n=2, Radiologists n=2) will view the randomised images under standardised conditions. The examiners will also be trained on how to interpret CBCT data before looking at images. The restorations will be assessed clinically.

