4.1.1 Primary Efficacy Parameters

The primary efficacy parameter will be the success of teeth in relation to the absence of any signs and symptoms, endodontic or restorative failures.

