4.2 Procedures for Assessing Efficacy Parameters

Patients will be recalled after 12 and 24 months for clinical and radiographical assessments. Four examiners other than the operator independently performed evaluation of success or failure.

Clinical examination should reveal the absence of the following events which considered if present as 'relative' failures: restoration debonding, restoration fracture, failure of the core portion requiring a new coronal restoration, and no mobility of the teeth or tenderness to percussion. While root fractures leading to tooth extraction were considered as 'absolute' failures.

CBCT scans assessment should reveal the absence or reduction of any radiolucencies or widening of the apical periodontal ligament space and vertical or horizontal root fracture.

5. Assessment of Safety

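### Image readers are not said to be masked to the residual-dentin group, and random image order does not mask it, although the apical score they give feeds the primary success outcome

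*Protocol*

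**What the plan says.** **Exposure.** Protocol section 2.2 has patients "divided into groups defined according to the residual coronal dentin after root canal treatment into four groups", with cut-points at 33%, 50% and 66%. The same sentence says that patients are grouped on clinical and radiographic assessment ("Patients requiring endodontic treatment will be assessed clinically and radiographically and divided into groups"). Section 2.4.3 confirms that patients are not randomised.

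**Images.** In section 1, "we would also take an additional specialised 3-dimensional Cone Beam Computed Tomography (CBCT) scan of the tooth". Section 2.2 adds that "Dental periapical radiograph and Cone Beam Computed Tomography (CBCT) scans will be taken at baseline, 12 months and 24 months". No field of view is given, and no cropping or covering of the crown is described.

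**Readers.** Section 2.2: "Four examiners (Endodontists n=2, Radiologists n=2) will view the randomised images under standardised conditions". Section 4.2: "Four examiners other than the operator independently performed evaluation of success or failure". Section 2.2 also says that the readers are trained in CBCT interpretation.

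**What they score.** Section 4.2: "CBCT scans assessment should reveal the absence or reduction of any radiolucencies or widening of the apical periodontal ligament space". No scoring index, threshold or rule for combining four readers is given. Section 4.1.1 makes this part of the primary outcome: "The primary efficacy parameter will be the success of teeth in relation to the absence of any signs and symptoms, endodontic or restorative failures". Section 2.4.4 compares success between the groups with a chi-square test.

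**Masking.** Neither document mentions it. The SAP contains only a power statement.

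**The concern.** The exposure is a property of the tooth being imaged. A reader who sees a heavily restored crown can guess that little dentin remained. The protocol also supplies an expectation: the premolar study described in section 2.4.1 is reported as finding lower failure risk with one, two or three coronal walls than in teeth without ferrule.

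The apical criterion leaves borderline cases to judgement. If these are called failures more readily in teeth that look badly broken down, the scoring itself creates or inflates the association under test. All four readers could lean the same way, so consensus or averaging would not remove it. Because the groups are not randomised, objective outcome assessment is one of the few protections the design can have.

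**Working it through.** **1. Does random order mask the group?** Patients are not randomised (section 2.4.3), so the word in section 2.2 can only describe the images or their order. Shuffling removes order effects. It does not alter the content of an image.

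**2. Can the group be seen?** Three statements bear on this: the scan is of the tooth, grouping is partly radiographic, and no cropping is described. Together they make crown and restoration probably visible. They do not show that a reader could place a restored tooth in the right one of four bands at 12 or 24 months. Partial inference, enough to tell the extreme groups apart, is the most that can be claimed.

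**3. Number of evaluable teeth.** The protocol's four-group calculation reproduces. With noncentrality N × w², w = 0.35 and 3 degrees of freedom, N = 90 gives 80.5% power at the 5% level, and 90 / (1 − 0.25) = 120, as stated. The illustration therefore uses 90 teeth, split 23/23/22/22.

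**4. Failure rate.** The background section gives 14% to 16% for initial treatment. I use 15% in every group, so there is no true association. Expected failures are 0.15 × 90 = 13.5.

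**5. Distortion (assumed).** Scored failure falls in equal steps from the worst group to the best, with the mean kept at 15%.

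- *All failures distorted.* A 2:1 ratio gives 20 / 16.7 / 13.3 / 10%. A 3:1 ratio gives 22.5 / 17.5 / 12.5 / 7.5%.
- *Half of failures apical, only that half distorted.* The non-apical half stays at 7.5% in each group. At 2:1 the apical half is 10 / 8.3 / 6.7 / 5%, for totals of 17.5 / 15.8 / 14.2 / 12.5%. At 3:1 it is 11.25 / 8.75 / 6.25 / 3.75%, for totals of 18.75 / 16.25 / 13.75 / 11.25%.

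**6. Result.** Simulated rejection rate of the Pearson chi-square test (3 degrees of freedom, nominal 5%):

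| Scenario | False-positive rate |
|---|---|
| No distortion | about 4.5% |
| Half apical, 2:1 in that half | about 5.6% |
| Half apical, 3:1 in that half | about 7.3% |
| All failures, 2:1 | about 10% |
| All failures, 3:1 | about 18% |

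Repeat runs differ by a few tenths of a percentage point at most.

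**The case against.** **Safeguards exist.** The examiners are not the operator, read independently, are trained and work under standardised conditions. Patients carry anonymised numbers (section 2.4.2) and unique identifiers (section 9). This stands as far as it goes: it limits self-assessment, reading error and recognition of the patient. None of it conceals the group.

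**Visibility is inferred.** This also stands. A reader might conclude that examiners demonstrably see the exposure group. The documents do not support that: they give no field of view or viewing format, and a restoration may obscure how much dentin remained.

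**Most of the outcome is not an image reading.** Section 4.2 also counts debonding, restoration fracture, core failure, mobility, percussion tenderness and root fracture, and section 2.2 has restorations assessed clinically. A reader might take 10% to 18% as the expected false-positive rate. That would require every failure to be distorted, whereas the avoidable bias lies in the apical part. The smaller figures are the more relevant ones.

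**Cropping may not mask an examiner who also sees the patient.** Sections 2.2 and 4.2 can be read as the same examiners doing both the clinical and the image assessment. This stands, and the remedy has to set the order of the two.

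**Cost.** With 120 teeth, three time points and four readers there are up to 120 × 3 × 4 = 1,440 CBCT reads, and a two-step read means up to 2,880 viewings in a self-funded study. The workload is real, but it needs no new scans or staff.

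**Conclusion.** The concern holds in a limited form. The plan does not say that image readers are masked, random order does not mask them, and the apical score is a judgement that feeds the primary outcome and can be made without the crown. Following the plan as written leaves an avoidable route to bias.

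Its size cannot be derived from the documents. If half of failures are apical and the distortion is confined to them, the false-positive rate rises from about 4.5% to between 5.6% and 7.3%; the larger figures are an upper illustration. The apical share, the 2:1 and 3:1 ratios and the graded pattern are all assumptions. The sample size is unaffected. This should be corrected, but it does not by itself invalidate the study.

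**What to change.** In sections 2.2 and 4.2:

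- State that image readers are masked to exposure group and to clinical data.
- Supply coded CBCT and periapical views, cropped or covered above the cervical level, for the apical score. Treat the baseline images in the same way, because judging a reduction needs a comparison.
- Lock the apical score before the full tooth is shown for root fracture, and before any clinical examination by the same examiner. Otherwise, use different people for the two tasks.
- State that the clinical assessment of the restoration cannot be masked.
- Report apical and restorative failures separately as well as combined, so that the maskable part can be judged alone.

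The cost is image preparation and a second viewing step for the same four readers. Posts or cores may still hint at the group, so masking will be partial.

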2.3 Trial Flowchart:-

2.4 Trial Statistics

2.4.1 Sample Size

The sample size calculation for this study was based on chi-test for testing the association between tooth surface lost (<33%, 33-66% and >66%) and Root Canal Treatment status (Success or Failure). A study with an effect size of 0.3 and a power of 80% will require a total sample of 108 to test the association at 5% levels using two tailed test. The power calculation was carried out using Gpower 3.1.7.

In a previous study by Ferrari et al. (2012), a sample of 345 patients provided 6 groups of 60 premolars each in need of endodontic treatment. Groups were classified according to the number of remaining coronal walls before abutment build-up. Within each group, teeth were allocated to one of three subgroups: (A) no post retention; (B) prefabricated post; or (C) customized posts (N = 20). The authors found that failure risk was lower in teeth restored with prefabricated ($p = 0.001$) than with customized posts ($p = 0.009$). Teeth with one ($p = 0.004$), two ($p < 0.001$), and three coronal walls ($p < 0.001$) had significantly lower failure risks than those without ferrule and similar failure risks existed for teeth without coronal walls, regardless of the presence/absence of ferrule ($p = 0.151$). Sample size calculation for this study was based on comparing success rates for the four groups using chi-square test. This study designed to have 80% power to detect the difference in success rates between the four groups at 5% level of significance with an effect size of 0.35 using a two-tailed test. Assuming a dropout rate of 25% at the end (after 2 years of root canal re-treatment), it requires a sample size of 120

2.4.2 Recruitment and Retention

Patients who have been referred to the Endodontic Postgraduate Unit or assessment clinics at King's College Dental Institute at Guy's Hospital for root canal treatment will first undergo an examination at the assessment clinic to diagnose and treatment plan their problem by the postgraduate students under supervision of the Consultants in charge of the Endodontic clinic. This is to check if the tooth is indicated for root canal treatment or extraction.

If they are indicated for root canal treatment and satisfies the inclusion criteria of the clinical trial, they will be given the invitation letter and Patient Information Sheet.

They then have about two weeks, before their scheduled appointment to decide if they want to take part in the study or not. If they express an interest, at this appointment, they will then be explained the study by the treating post graduate student, who is part of the research team and thereby begin the informed consent process. Consented patients will be allocated an anonymised number.

If they do not wish to take part, they will still receive routine treatment as planned at the assessment clinic

2.4.3 Randomisation

Randomisation is not applicable, as the patients will be divided according to the number of tooth structure lost.

2.4.4 Analysis

Descriptive statistics will be used to summarise the sample characteristics and baseline measurements. Chi square test for association will be used to test whether there is any relationship between success rate and different groups. The difference in success rate over a period of time will be analysed using survival analysis. This will involve Kaplan-Meier graph and cox regression predictors of failure rate. All analysis will be carried out by using SPSS version 20.

3. Selection and Withdrawal of Subjects

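### With about 13 to 19 failures at the quoted background rate, standard Cox regression on the four residual-structure groups may meet a group with no failures, and section 2.4.4 has no provision for it.

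*Protocol*

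**What the plan says.** Protocol section 2.4.4 plans descriptive statistics, a chi-square test of success against group, and survival analysis. On the last it says: "This will involve Kaplan-Meier graph and cox regression predictors of failure rate". It then adds: "All analysis will be carried out by using SPSS version 20". No covariates, coding, reference group or sparse-event method are given. The SAP contains only a power statement and does not mention the Cox model.

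The sample size in section 2.4.1 rests on chi-square tests alone. The four-group calculation has "80% power to detect the difference in success rates between the four groups at 5% level of significance". It takes w = 0.35 and allows for loss to follow-up: "Assuming a dropout rate of 25% at the end". No failure rate or number of failures is stated there.

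The only failure rate is in section 1, where published rates of 14-16% are cited "for initial root canal treatment". The trial's own failure definition, in sections 4.1.1 and 4.2, is wider. It covers signs and symptoms, debonding, restoration fracture, core failure, mobility, tenderness, root fracture and radiographic findings. No rate is given for that composite.

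**The concern.** The Cox model is the plan's only stated way to express how residual structure, or any other predictor, relates to the hazard of failure. A four-level factor takes three parameters. If a group has no failures, the partial likelihood keeps increasing as that group's log hazard goes to minus infinity. Software then reports a huge or non-converged estimate with a meaningless Wald interval.

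If the empty group is the reference, the same happens to all three contrasts. Under a gradient the group with more than 66% remaining is the likeliest to be empty, and it is also a natural reference to choose. The plan leaves that choice open. The difficulty is greatest when the effect that the trial is powered to find is real, because a strong effect means very few failures in the better groups.

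**Working it through.** **Inputs.** From section 2.4.1: 120 enrolled, 25% dropout, w = 0.35, 80% power, 5% level. From section 2.2: four groups. From section 1: 14-16% failure (background). Assumed here: equal groups, one tooth per patient, and dropouts contributing no failures in the 90-tooth case.

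**The plan's own figures.** Power of the chi-square test uses noncentrality N × w².
- w = 0.35 with 3 degrees of freedom needs N = 90 (power 0.805). Then 90 / (1 − 0.25) = 120, as stated.
- w = 0.3 with 2 degrees of freedom needs N = 108 (power 0.804), as stated, with no dropout allowance.

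**Expected failures** = N × rate.
- N = 90: 90 × 0.14 = 12.6 to 90 × 0.16 = 14.4.
- N = 120: 120 × 0.14 = 16.8 to 120 × 0.16 = 19.2.
- Per parameter of the group factor: 12.6 / 3 = 4.2 to 19.2 / 3 = 6.4, before any other predictor.

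**Chance of at least one empty group** = 1 − ∏[1 − (1 − p_g)^n_g], with n = 23/23/22/22 or 30 each.

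Worked case: failure rates 35.6/13.6/8.1/2.7%, with mean m = 15%.
- Effect size: w = √(mean squared deviation / [m(1 − m)]) = √(0.01563 / 0.1275) = 0.35.
- Chance of no failures in each group at N = 90: 0.644^23 ≈ 0.000; 0.864^23 = 0.035; 0.919^22 = 0.156; 0.973^22 = 0.548.
- Result: 1 − (1.000 × 0.965 × 0.844 × 0.452) = 0.63.

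All patterns at a 15% mean rate:

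| Failure rates by group (%) | w | N = 90 | N = 120 |
|---|---|---|---|
| 36.6/7.8/7.8/7.8 | 0.35 | 41% | 24% |
| 35.6/13.6/8.1/2.7 | 0.35 | 63% | 49% |
| 27.5/27.5/2.5/2.5 | 0.35 | 82% | 72% |
| 30/15/10/5 | 0.26 | 40% | 25% |
| 15/15/15/15 | 0 | 10% | 3% |

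**Sensitivity to the overall rate**, with w = 0.35 and rates linear on the log-odds scale across groups:

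| Mean failure rate | N = 90 | N = 120 |
|---|---|---|
| 15% | about 68% | about 55% |
| 20% | about 38% | about 25% |
| 25% | about 19% | about 10% |
| 30% | about 8% | about 3% |

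Using 22.5 per group instead of 23/23/22/22 moves these by about one percentage point at most. The 20-30% rates are assumptions, because the documents give no composite rate.

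**Which group is empty.** Under the 15% gradient with 90 evaluable, the best group has no failures about 57% of the time and the worst about 0.01%. The choice of reference therefore decides whether one contrast is lost or all three.

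**Unequal groups.** Section 2.4.3 says patients are grouped by tooth structure rather than randomised, so equal sizes are not assured. With sizes 9/18/27/36 and no effect, the chance is already 25-32% at rates of 16% down to 14%.

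**The case against.** The strongest reply is that 14-16% is a literature figure for root canal treatment and not a design assumption. The trial counts restorative and clinical failures as well, so its rate may be higher, and the second table shows how much that matters. This stands, and every probability above is conditional on the rate. At 20% the risk is still material (38% and 25%). It becomes small only towards 30%.

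It is also fair that w = 0.35 is a large effect. At a 15% rate and w = 0.20, the gradient gives 29% and 16%. The 82% and 72% come from a two-high, two-low pattern that no document proposes.

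The four-level factor in the Cox model is an inference. Section 2.4.4 does not list it, and the other power statement, repeated in the SAP, uses three categories. The inference is reasonable, since the objective concerns residual structure and section 2.2 defines four groups. With three groups of 30, w = 0.3 and a 15% rate, a gradient still gives about 32%.

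A reader might infer that the Cox hazard ratios cannot be estimated at all. The documents do not support that. If the empty group is not the reference, only its own ratio lacks a finite estimate and the other contrasts remain. Likelihood-ratio and log-rank tests also stay usable. A reader might also infer that overfitting is proven. It is not, because the predictors are not listed and an empty group is a different problem from overfitting.

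**Conclusion.** The concern holds conditionally. If the composite failure rate is near 15%, groups are about equal, residual structure enters as four groups and the planned effect is true, the chance of an empty group is roughly 40-80% with 90 evaluable teeth and 25-70% with 120. With no group effect it is about 10% and 3%, and higher overall rates reduce it as tabulated. The consequence is one unusable hazard ratio, or three if the reference group is the empty one.

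It would go too far to conclude that the trial could not answer its main question. The chi-square test on which the study is sized and the Kaplan-Meier curves both work with an empty group. What is affected is the hazard-ratio analysis, for which a better method is available at little cost and can be fixed in advance.

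**What to change.** In section 2.4.4:
- Fit the Cox model by Firth-penalised partial likelihood with profile-likelihood intervals, which give finite estimates when a group has no failures.
- State that residual structure enters as the four-group factor, with under 33% remaining as reference. Say explicitly that this is structure remaining, because the three-category power statement is worded in terms of loss.
- Limit further predictors to one or two, named in advance.
- Amend the SPSS-only sentence so that another package may be used for this model.

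A one-degree-of-freedom trend across the ordered groups may be added as a supplementary analysis. It should not replace the group factor. It assumes a steady gradient, and the earlier study described in section 2.4.1 found similar failure risks in teeth without coronal walls whether or not a ferrule was present (p = 0.151). A model on measured percentage is not proposed, because section 2.2 promises only categories.

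The cost is a change of analysis wording, a different software routine and slight shrinkage of the estimates. Sample size, visits and procedures do not change.
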